### 14.3.2 Listing of Deaths, Other Serious and Significant Adverse Events

**Table 36: Listing of Serious Adverse Events**

Adverse Event	No. of Days Post Dose (Duration)	No. of Days Post Dose the Event Became Serious	Reason Reported as an SAE	Severity	Relationship to Study Treatment	If Not Related, Alternative Etiology	Action Taken with Study Treatment	Participant Discontinued Due to AE	MAAE/ NOCMC/ UP?	Outcome	MedDRA System Organ Class	MedDRA High Level Group Term	MedDRA Preferred Term
Dose Cohort:, Participant ID:, AE Number:													
Comments:													
Dose Cohort:, Participant ID:, AE Number:													
Comments:													

**Table 37: Listing of Non-Serious, Unsolicited, Moderate or Severe Adverse Events**

[Implementation note: All Non-Serious AEs, which are greater than grade 2, will be included.]

Adverse Event	No. of Days Post Dose (Duration)	Severity	Relationship to Study Treatment	If Not Related, Alternative Etiology	Action Taken with Study Treatment	Participant Discontinued Due to AE	Outcome	MedDRA System Organ Class	MedDRA High Level Group Term	MedDRA Preferred Term
Dose Cohort:, Participant ID:, AE Number:										
Comments:										
Dose Cohort:, Participant ID:, AE Number:										
Comments:										

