### 9.3.2. **Unsolicited Adverse Events**

Unsolicited AEs will be collected from the time of infusion through Day 29. Unsolicited AEs will be coded by MedDRA for PT, HLT, and SOC. The proportion of participants reporting at least one unsolicited AE will be summarized by MedDRA SOC, HLT and PT post infusion. Denominators for percentages are the number of participants who received the infusion being summarized.

AEs by participant will be presented in Listing 12.

The following summaries for unsolicited AEs will be presented by MedDRA SOC, HLT, PT, and Dose Cohort:

- The incidence and total frequency of AEs with Pearson-clopper 95% CI (Table 32)
- Summary of maximum severity and relationship to study product (Table 33 and Table 34)
- Participant incidence and total frequency of related adverse events by Dose Cohort (Table 35)
- Participant listing of serious AEs (Table 36)
- Participant listing of non-serious AEs of moderate or severe grade (Table 37)
- Listing of other significant AEs (Table 38)
- Listing of Unanticipated Problems (UPs) (Table 39, Table 40)
- Bar chart of non-serious related AEs by severity and MedDRA SOC (Figure 4)
- Bar chart of non-serious related AEs by maximum severity and MedDRA SOC (Figure 5)

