## 9.4. Deaths, Serious Adverse Events and other Significant Adverse Events

The following listings will be presented including Participant ID, Age (years), Adverse Event Description, Adverse Event Onset Date/End Date, Dose Received/Days Post Dose, Reason Reported as an SAE, Relationship to Treatment, Alternate Etiology if not Related, Outcome, and Duration of Event (days):

- Deaths and Serious Adverse Events ([Table 36](#))
- Non-serious unsolicited, moderate or severe AEs, which are grade 2 or more ([Table 37](#))

Other significant AEs, including NOCMCs, MAAEs, ([Table 38](#)) and UPs ([Table 39](#), [Table 40](#)).

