## 14.3 Safety Data

### 14.3.1 Displays of Adverse Events

**Table 23: Overall Summary of Adverse Events**

	3 mg/kg EV68-228-N (N=X)		10 mg/kg EV68-228-N (N=X)		30 mg/kg EV68-228-N (N=X)		Placebo (N=X)		All Participants who Received Active Product (N = x)	
Participants a with	n	%	n	%	n	%	n	%	n	%
At least one solicited adverse event	x	xx	x	xx	x	xx	x	xx	x	xx
At least one unsolicited adverse event	x	xx	x	xx	x	xx	x	xx	x	xx
At least one related unsolicited adverse event	x	xx	x	xx	x	xx	x	xx	x	xx
Mild (Grade 1)	x	xx	x	xx	x	xx	x	xx	x	xx
Moderate (Grade 2)	x	xx	x	xx	x	xx	x	xx	x	xx
Severe (Grade 3)	x	xxx	x	xx	x	xx	x	xx	x	xx
Life-threatening (Grade 4)	x	xx	x	xx	x	xx	x	xx	x	xx
Death (Grade 5)										
At least one severe (Grade 3 or higher) unsolicited adverse event										
Related										
Unrelated										
At least one serious adverse event b										
At least one related, serious adverse event										
At least one adverse event leading to early termination c										
At least one unanticipated problem (UPs)										
At least one medically attended adverse event (MAAEs)										
At least one new onset chronic medical conditions (NOCMCs)										

Note: N=Number of participants in the Safety Population.

a Participants are counted once for each category regardless of the number of events.

b A listing of Serious Adverse Events is included in Section 14.3.2.

c As reported on the Adverse Event eCRF.

**Table 24: Adverse Events Occurring in  $\geq 5\%$  of Participants in Any Dose Cohort by MedDRA System Organ Class and Preferred Term and Dose Cohort**

[Implementation Note: This table will report both solicited and unsolicited AEs.]

MedDRA System Organ Class	MedDRA Preferred Term	3 mg/kg EV68-228-N (N=X)			10 mg/kg EV68-228-N (N=X)			30 mg/kg EV68-228-N (N=X)			Placebo (N=X)			All Participants who Received Active Product (N=X)		
		n	%	Events	n	%	Events	n	%	Events	n	%	Events	n	%	Events
Serious Adverse Events																
All	All	x	xx	x	x	xx	x	x	xx	x	x	xx	x	x	xx	x
SOC1	All															
	PT1															
	Etc.															
	All															
	PT1	x	xx	x	x	xx	x	x	xx	x	x	xx	x	x	xx	x
Etc.	Etc.															
Other (Non-serious) Adverse Events																
All	All	x	xx	x	x	xx	x	x	xx	x	x	xx	x	x	xx	x
SOC1	All	x	xx	x	x	xx	x	x	xx	x	x	xx	x	x	xx	x
	PT1															
	Etc.															
Etc	Etc															

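### The Table 37 programming note selects AEs above Grade 2 and omits the restriction to unsolicited events, contradicting the table's title and SAP Section 9.4

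*SAP*

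**What the plan says.** The SAP describes the content of Table 37 in four places.

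- **Section 9.3.2 (Unsolicited Adverse Events)** lists it among the unsolicited-event outputs: "Participant listing of non-serious AEs of moderate or severe grade".
- **Section 9.4** points to it and gives an explicit threshold: "Non-serious unsolicited, moderate or severe AEs, which are grade 2 or more".
- **The table title** reads "Listing of Non-Serious, Unsolicited, Moderate or Severe Adverse Events".
- **The implementation note under that title** reads "All Non-Serious AEs, which are greater than grade 2, will be included".

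Table 23 fixes how severity words map to grades. Its rows include "Moderate (Grade 2") and "Severe (Grade 3"), followed by life-threatening as Grade 4 and death as Grade 5.

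**The concern.** The note is the only selection rule printed in the Table 37 shell, and it disagrees with the title directly above it and with both body sections. A programmer working from the shell could reasonably code the filter as grade above 2.

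The output would then be headed as moderate or severe events but could contain no moderate ones. A reader of that page alone might conclude that no non-serious moderate event had occurred. In a first-in-human trial with 10 active participants per dose (Table 1), individual events get close attention, so a listing whose content does not match its title is worth correcting before programming.

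The same sentence also leaves out the limit to unsolicited events. Solicited AEs are collected and displayed separately (Section 9.3.1, Tables 25 to 31, Listing 11). Read literally, the note would let a severe solicited symptom into a table titled for unsolicited events.

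**Working it through.** No sample-size or estimation figure is involved, so the check compares the event sets that each statement selects.

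**Mapping (Table 23).** Moderate = Grade 2, severe = Grade 3, life-threatening = Grade 4. Grade 5 is death and cannot be non-serious, so the grades in play for Table 37 are 2, 3 and 4.

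| Place in the SAP | Rule | Grades selected | Limited to unsolicited? |
|---|---|---|---|
| Section 9.3.2 | moderate or severe | 2, 3 | yes, by its section |
| Section 9.4 | grade ≥ 2 | 2, 3, 4 | yes |
| Table 37 title | moderate or severe | 2, 3 | yes |
| Table 37 note | grade > 2 | 3, 4 | not stated |

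**Grade.** Section 9.4 minus the note is {2, 3, 4} − {3, 4} = {2}. The difference is the whole moderate stratum. The first three rows all include Grade 2; only the note excludes it.

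**Event type.** Title and Section 9.4: unsolicited only. Note: all non-serious AEs. The literal excess is non-serious solicited AEs of Grade 3 or 4.

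**Status of the text.** The note is a complete sentence in the current version. The version history records one change for version 2.0, a table number and title on a continuation page of Table 34, so the conflict was not addressed there.

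**Where a Grade 2 unsolicited event would still appear.**

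- Table 32: counted among all unsolicited AEs, with percentage, exact 95% CI and number of events.
- Table 33: a moderate row within each MedDRA category.
- Table 34: the same, split by relationship to study product.
- Listing 12: the individual record. Table 37 has 11 columns (event, days post dose with duration, severity, relationship, alternative etiology, action taken, discontinuation, outcome and three MedDRA levels). Listing 12 has all 11, plus SAE and MAAE/NOCMC/UP flags.
- Table 38: also, if the event is an MAAE or NOCMC.

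The primary outcome measures in Section 3.2.1 are proportions of participants with events. None is computed from Table 37.

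**The case against.** The strongest reply is that the intended rule is not in doubt and nothing of substance depends on the slip. Three statements agree, Section 9.4 gives the threshold in so many words, and the SAP nowhere says that shell notes override body text. A listing titled moderate or severe with no moderate entries would clash visibly with the moderate rows of Table 33, so routine checking might well catch it. The missing word unsolicited can be read as supplied by the title just above.

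Most of this stands. It lowers the chance of harm and shows that the right answer is already in the document. It does not make the note correct: one output has two incompatible filters, and a correct result would depend on someone overriding a written instruction.

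A reader might infer more, namely that the CSR as a whole would understate moderate events. The documents do not support that. The same events are counted in Tables 32 to 34 and listed with the same detail in Listing 12. Nor does the SAP give Table 37 special standing among the safety listings. Saying that all Grade 2 events would be missing from the table only restates the filter; it does not measure an effect on any estimate.

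**Conclusion.** The inconsistency is real and the note is wrong as written. Applied literally, Table 37 would omit every non-serious Grade 2 unsolicited event and could include solicited events of Grade 3 or higher, so its content would not match its title.

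The consequence is limited to that listing. No proportion, confidence interval or primary safety endpoint changes, and no event is lost from the report. How many records would be affected cannot be known from the SAP.

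This rests on two assumptions: that the programmer follows the note rather than Section 9.4, and that AE grades are whole numbers mapped as in Table 23. It is an internal inconsistency in a table shell, of minor severity. The choice of analysis is not at issue.

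**What to change.** Replace the Table 37 implementation note with: *All non-serious unsolicited AEs of Grade 2 or higher will be included.* This takes the threshold and the event type from Section 9.4 and needs no new judgement.

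The cost is one line in a table shell. Design, data collection and every other output are unaffected.

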**Table 38: Listing of Other Significant Adverse Events**

[Implementation Note: Other Significant Adverse Events include New Onset Chronic Medical Conditions (NOCMC), Medically Attended Adverse Events (MAAEs).]

Adverse Event	No. of Days Post Dose (Duration)	Severity	Relationship to Study Treatment	If Not Related, Alternative Etiology	Action Taken with Study Treatment	Participant Discontinued Due to AE	Outcome	MAAE/ NOCMC/ UP?	MedDRA System Organ Class	MedDRA High Level Group Term	MedDRA Preferred Term
Dose Cohort:, Participant ID:, AE Number:											
Comments:											

**Table 39: Listing of Participant-Specific Unanticipated Problems (UPs)**

[Implementation note: “Study Day” is relative to treatment administration; the day of treatment administration is Day 1, and the day prior to treatment administration is Day -1.

If event is an AE, display “Yes” followed by the AE description and number separated by a semicolon in parentheses.

If event is a PD, display “Yes” followed by the deviation description and number separated by a semicolon in parentheses.

If there are no comments, display “None” in the “Comments” column. If there are no comments for any UPs in the listing, remove the “Comments” column. If the comments are too long to display in the “Comments” column, the format of this table may be updated to remove the “Comments” column.

Sort by Dose Cohort, Participant ID, and UP Number.]

Dose Cohort	Participant ID	UP number	Event Description	Event Outcome	Study Day of Site Awareness	Study Day Reported to Sponsor/DCC	Study Day Reported to IRB	Is the event an AE (AE Description; Number)	Is the event an PD (DV Description; Number)	Comments
3 mg/kg EV68-228-N	zzz.XXXXX	xxx	[description]	[outcome]	x	x	x	No	No	
10 mg/kg EV68-228-N								Yes ([description]; XXX)	Yes ([description]; XXX)	
30 mg/kg EV68-228-N										

Abbreviations: UP = Unanticipated Problem; DCC – Data Coordinating Center; IRB = Institutional Review Board; AE = Adverse Event; PD = Protocol Deviation; DV = Deviation.

**Table 40: Listing of Non-Participant Specific Unanticipated Problems (UPs)**

[implementation note:

If event is a PD, display “Yes” followed by the deviation description and number separated by a semicolon in parentheses.

If there are no comments, display “None” in the “Comments” column. If there are no comments for any UPs in the listing, remove the “Comments” column. If the comments are too long to display in the “Comments” column, the format of this table may be updated to remove the “Comments” column.

Sort by Site and UP Number]

Site	UP number	Event Description	Event Outcome	Event Date	Date of Site Awareness	Study Day Reported to Sponsor/DCC	Study Day Reported to IRB	Is the event an PD (DV Description Number)	Comments
University of Maryland	xxx	[description]	[outcome]	DDMMYYYY	DDMMYYYY	DDMMYYYY	DDMMYYYY	No	
Vanderbilt University								Yes ([description]; XXX)	

Abbreviations: UP = Unanticipated Problem; DCC – Data Coordinating Center; IRB = Institutional Review Board; AE = Adverse Event; PD = Protocol Deviation; DV = Deviation.

#### **14.3.3 Narratives of Deaths, Other Serious and Significant Adverse Events**

Not included in SAP, but this is a placeholder for the CSR.

**14.3.4 Abnormal Laboratory Value Listings (by Participant)****Table 41: Listing of Abnormal Laboratory Results – Chemistry**

Dose Cohort	Participant ID	Sex	Age (years)	Planned Time Point	Actual Study Day	Laboratory Parameter (Units)	Result (Severity)	Relationship to Treatment	If Not Related, Alternate Etiology	Clinically Significant?	Participation Discontinued Due to Result?

**Table 42: Listing of Abnormal Laboratory Results – Hematology**

Dose Cohort	Participant ID	Sex	Age (years)	Planned Time Point	Actual Study Day	Laboratory Parameter (Units)	Result (Severity)	Relationship to Treatment	If Not Related, Alternate Etiology	Clinically Significant?	Participant Discontinued Due to Result?

**Table 43: Listing of Abnormal Laboratory Results – Hypersensitivity**

Dose Cohort	Participant ID	Sex	Age (years)	Planned Time Point	Actual Study Day	Parameter	Units	Result	Clinically Significant?
				Baseline/ Onset of symptom/ 2 or more hours after onset/ Resolution of symptom		Complement Component 3/ Complement Component 4/ CH50/ Immunoglobulin E/ Serum Tryptase		x	CS/NCS

### 14.3.5 Displays of Laboratory Results

#### 14.3.5.1 Chemistry Results

**Table 44: Laboratory Results by Parameter, Maximum Severity, Time Point, and Dose Cohort – Any Chemistry Parameter**

[Implementation note: we assume there are no missing grade, so removed the column "missing" from the table, if any missing found, we will add footnote to the table]

Any Chemistry Parameter Time Point	Dose Cohort	N	None		Mild/ Grade 1		Moderate/ Grade 2		Severe/ Grade 3		Life-threatening/ Grade 4	
			n	%	n	%	n	%	n	%	n	%
Baseline	3 mg/kg EV68-228-N	x	x	xx	x	xx	x	xx	x	xx	x	xx
	10 mg/kg EV68-228-N											
	30 mg/kg EV68-228-N											
	Placebo											
Day 2	3 mg/kg EV68-228-N											
	10 mg/kg EV68-228-N											
	30 mg/kg EV68-228-N											
	Placebo											
Day 3	3 mg/kg EV68-228-N											
	10 mg/kg EV68-228-N											
	30 mg/kg EV68-228-N											
	Placebo											
Day 8	3 mg/kg EV68-228-N											
	10 mg/kg EV68-228-N											
	30 mg/kg EV68-228-N											
	Placebo											
Day 29	3 mg/kg EV68-228-N											
	10 mg/kg EV68-228-N											
	30 mg/kg EV68-228-N											
	Placebo											

**Table 44: Laboratory Results by Parameter, Maximum Severity, Time Point, and Dose Cohort – Any Chemistry Parameter (continued)**

Any Chemistry Parameter Time Point	Dose Cohort	N	None		Mild/ Grade 1		Moderate/ Grade 2		Severe/ Grade 3		Life-threatening/ Grade 4	
			n	%	n	%	n	%	n	%	n	%
Max Severity Post Baseline	3 mg/kg EV68-228-N											
	10 mg/kg EV68-228-N											
	30 mg/kg EV68-228-N											
	Placebo											

Notes: The “Max Severity Post Baseline” rows indicate the maximum severity experienced by each participant at any time point post baseline, including unscheduled assessments. N=Number of participants in the Safety Population.

**Table 45: Laboratory Results by Parameter Time Point, and Dose Cohort – Chemistry: Creatinine**

[Implementation note: we assume there are no missing grade, so removed the column "missing" from the table, if any missing found, we will add footnote to the table]

Creatinine Time Point	Dose Cohort	N	None		Mild/ Grade 1		Moderate/ Grade 2		Severe/ Grade 3		Life-threatening/ Grade 4	
			n	%	n	%	n	%	n	%	n	%
Baseline	3 mg/kg EV68-228-N	x	x	xx	x	xx	x	xx	x	xx	x	xx
	10 mg/kg EV68-228-N											
	30 mg/kg EV68-228-N											
	Placebo											
Day 2	3 mg/kg EV68-228-N											
	10 mg/kg EV68-228-N											
	30 mg/kg EV68-228-N											
	Placebo											
Day 3	3 mg/kg EV68-228-N											
	10 mg/kg EV68-228-N											
	30 mg/kg EV68-228-N											
	Placebo											
Day 8	3 mg/kg EV68-228-N											
	10 mg/kg EV68-228-N											
	30 mg/kg EV68-228-N											
	Placebo											
Day 29	3 mg/kg EV68-228-N											
	10 mg/kg EV68-228-N											
	30 mg/kg EV68-228-N											
	Placebo											

**Table 45: Laboratory Results by Parameter Time Point, and Dose Cohort – Chemistry: Creatinine (continued)**

Creatinine Time Point	Dose Cohort	N	None		Mild/ Grade 1		Moderate/ Grade 2		Severe/ Grade 3		Life-threatening/ Grade 4	
			n	%	n	%	n	%	n	%	n	%
Max Severity Post Baseline	3 mg/kg EV68-228-N											
	10 mg/kg EV68-228-N											
	30 mg/kg EV68-228-N											
	Placebo											

Notes: The “Max Post Baseline” rows indicate the maximum severity experienced by each participant at any time point post baseline, including unscheduled assessments. N=Number of participants in the Safety Population.

Tables with similar format:

**Table 46: Laboratory Results by Parameter Time Point, and Dose Cohort – Total Bilirubin****Table 47: Laboratory Results by Parameter Time Point, and Dose Cohort – ALT**

**Table 48: Laboratory Results Related to Study Treatment by Parameter, Maximum Severity, Time Point, and Dose Cohort – Any Chemistry Parameter**

[Implementation note: we assume there are no missing grade, so removed the column "missing" from the table, if any missing found, we will add footnote to the table]

Any Chemistry Parameter Time Point	Dose Cohort	N	None		Mild/ Grade 1		Moderate/ Grade 2		Severe/ Grade 3		Life-threatening/ Grade 4	
			n	%	n	%	n	%	n	%	n	%
Baseline	3 mg/kg EV68-228-N	x	x	xx	x	xx	x	xx	x	xx	x	xx
	10 mg/kg EV68-228-N											
	30 mg/kg EV68-228-N											
	Placebo											
Day 2	3 mg/kg EV68-228-N											
	10 mg/kg EV68-228-N											
	30 mg/kg EV68-228-N											
	Placebo											
Day 3	3 mg/kg EV68-228-N											
	10 mg/kg EV68-228-N											
	30 mg/kg EV68-228-N											
	Placebo											
Day 8	3 mg/kg EV68-228-N											
	10 mg/kg EV68-228-N											
	30 mg/kg EV68-228-N											
	Placebo											
Day 29	3 mg/kg EV68-228-N											
	10 mg/kg EV68-228-N											
	30 mg/kg EV68-228-N											
	Placebo											

**Table 48: Laboratory Results Related to Study Treatment by Parameter, Maximum Severity, Time Point, and Dose Cohort – Any Chemistry Parameter (continued)**

Any Chemistry Parameter Time Point	Dose Cohort	N	None		Mild/ Grade 1		Moderate/ Grade 2		Severe/ Grade 3		Life-threatening/ Grade 4	
			n	%	n	%	n	%	n	%	n	%
Max Severity Post Baseline	3 mg/kg EV68-228-N											
	10 mg/kg EV68-228-N											
	30 mg/kg EV68-228-N											
	Placebo											

Notes: The “Max Post Baseline” rows indicate the maximum severity experienced by each participant at any time point post baseline, including unscheduled assessments. N=Number of participants in the Safety Population

Tables with similar format:

**Table 49: Laboratory Results Related to Study Treatment by Parameter, Maximum Severity, Time Point, and Dose Cohort – Creatinine****Table 50: Laboratory Results Related to Study Treatment by Parameter, Maximum Severity, Time Point, and Dose Cohort – Total Bilirubin****Table 51: Laboratory Results Related to Study Treatment by Parameter, Maximum Severity, Time Point, and Dose Cohort – ALT**

**Table 52: Laboratory Summary Statistics by Parameter, Time Point, and Dose Cohort – Creatinine**

Time Point	Dose Cohort	N	Mean	Standard Deviation	Median	Min, Max
Baseline	3 mg/kg EV68-228-N	x	xx.x	xx.x	xx.x	xx.x, xx.x
	10 mg/kg EV68-228-N					
	30 mg/kg EV68-228-N					
	Placebo					
Day 2	3 mg/kg EV68-228-N	x	xx.x	xx.x	xx.x	xx.x, xx.x
	10 mg/kg EV68-228-N					
	30 mg/kg EV68-228-N					
	Placebo					
Day 2, Change from Baseline	3 mg/kg EV68-228-N	x	xx.x	xx.x	xx.x	xx.x, xx.x
	10 mg/kg EV68-228-N					
	30 mg/kg EV68-228-N					
	Placebo					
Day 3	3 mg/kg EV68-228-N	x	xx.x	xx.x	xx.x	xx.x, xx.x
	10 mg/kg EV68-228-N					
	30 mg/kg EV68-228-N					
	Placebo					
Day 3, Change from Baseline	3 mg/kg EV68-228-N	x	xx.x	xx.x	xx.x	xx.x, xx.x
	10 mg/kg EV68-228-N					
	30 mg/kg EV68-228-N					
	Placebo					
Day 8	3 mg/kg EV68-228-N	x	xx.x	xx.x	xx.x	xx.x, xx.x
	10 mg/kg EV68-228-N					
	30 mg/kg EV68-228-N					
	Placebo					
Day 8, Change from Baseline	3 mg/kg EV68-228-N	x	xx.x	xx.x	xx.x	xx.x, xx.x
	10 mg/kg EV68-228-N					
	30 mg/kg EV68-228-N					
	Placebo					
Day 29	3 mg/kg EV68-228-N	x	xx.x	xx.x	xx.x	xx.x, xx.x
	10 mg/kg EV68-228-N					
	30 mg/kg EV68-228-N					
	Placebo					
Day 29, Change from Baseline	3 mg/kg EV68-228-N	x	xx.x	xx.x	xx.x	xx.x, xx.x
	10 mg/kg EV68-228-N					
	30 mg/kg EV68-228-N					
	Placebo					

Note: N=Number of participants in the Safety Population with non-missing values at respective visit.

Tables with similar format:

**Table 53: Laboratory Summary Statistics by Parameter, Time Point, and Dose Cohort – Total Bilirubin**

**Table 54: Laboratory Summary Statistics by Parameter, Time Point, and Dose Cohort – ALT**

**14.3.5.2 Hematology Results****Table 55: Laboratory Results by Parameter, Maximum Severity, Time Point, and Dose Cohort – Any Hematology Parameter**

[Implementation note: we assume there are no missing grade, so removed the column "missing" from the table, if any missing found, we will add footnote to the table]

Any Hematology Parameter Time Point	Dose Cohort	N	None		Mild/ Grade 1		Moderate/ Grade 2		Severe/ Grade 3		Life-threatening/ Grade 4	
			n	%	n	%	n	%	n	%	n	%
Baseline	3 mg/kg EV68-228-N	x	x	xx	x	xx	x	xx	x	xx	x	xx
	10 mg/kg EV68-228-N											
	30 mg/kg EV68-228-N											
	Placebo											
Day 2	3 mg/kg EV68-228-N											
	10 mg/kg EV68-228-N											
	30 mg/kg EV68-228-N											
	Placebo											
Day 3	3 mg/kg EV68-228-N											
	10 mg/kg EV68-228-N											
	30 mg/kg EV68-228-N											
	Placebo											
Day 8	3 mg/kg EV68-228-N											
	10 mg/kg EV68-228-N											
	30 mg/kg EV68-228-N											
	Placebo											
Day 29	3 mg/kg EV68-228-N											
	10 mg/kg EV68-228-N											
	30 mg/kg EV68-228-N											
	Placebo											

**Table 55: Laboratory Results by Parameter, Maximum Severity, Time Point, and Dose Cohort – Any Hematology Parameter (continued)**

Any Hematology Parameter Time Point	Dose Cohort	N	None		Mild/ Grade 1		Moderate/ Grade 2		Severe/ Grade 3		Life-threatening/ Grade 4	
			n	%	n	%	n	%	n	%	n	%
Max Severity Post Baseline	3 mg/kg EV68-228-N											
	10 mg/kg EV68-228-N											
	30 mg/kg EV68-228-N											
	Placebo											

Notes: The “Max Post Baseline” rows indicate the maximum severity experienced by each participant at any time point post baseline, including unscheduled assessments. N=Number of participants in the Safety Population.

Tables with similar format:

